6.3. Other Endpoints

Baseline characteristics, including gender, race, ethnicity, alcohol and tobacco use, cardiovascular risk factors, primary diagnosis, time since primary diagnosis, and medical history will be collected prior to randomization. The collection of primary diagnosis and time since primary diagnosis was originally collected, but discontinued following a change to the CRF.

Concomitant and pre-study medications and non-drug treatments, including statins and non-statin lipid lowering treatments, will be collected throughout the study.

The date and time of each dose of study medication and the number of injections will be collected, as will reasons for discontinuation from study therapy and from the study. Treatment duration will be calculated as (the date of last active dose – the date of first active dose +15).

After the randomization visit, subjects will be directed to bring any used and unused syringe cartons to each visit. Used syringes will be returned to the study center in a biohazard container when it is full, to receive a new container, and when directed by the study site.

Compliance is calculated as the percent of planned Investigational Product (IP) doses that were actually taken. Cartons lost prior to the administration of IP, or damaged and unused syringes, should not be counted as completed dose administrations. From this information, compliance, based on the dosing schedule, will be calculated as follows:

$$\text{Compliance} = 100\% \times \frac{\text{actual dose administrations}}{\text{dose administrations planned}}$$

- The number of actual dose administrations will be derived from the dosing CRF page.
- For subjects who do not have two dose adjustments, the number of dose administrations planned is one plus the integer part of one-fourteenth of the number of days from randomization to the date the site instructs the subject to discontinue study medication. For subjects who have two dose adjustments, the number of dose administrations planned is one plus the integer part of one-fourteenth of the number of days from randomization to the visit at which the second dose adjustment takes place plus one-twenty-eighth the number of days from the visit at which the second dose adjustment takes place to the date the site instructs the subject to discontinue study medication.
- *In the event of an adverse event (AE) or reaction, subjects may be counseled to interrupt dosing permanently or temporarily. Doses not taken in such instances do not count as planned dose administrations and do not constitute lack of compliance.*

6.3.1. Pharmacokinetic/Pharmacodynamic Endpoints

Pharmacokinetic/Pharmacodynamic (PK/PD) endpoints include plasma bococizumab concentration. Samples will not be assayed for PCSK9.

Blood samples for bococizumab and PCSK9 will be collected as specified in the Schedule of Activities. On all bococizumab/PCSK9 blood sample collection days, samples must be collected prior to bococizumab dosing. After randomization, if lipid sampling has been postponed to an unscheduled visit, the corresponding ADA, PK, and PCSK9 samples should be postponed as well, and collected at the at the same time as the rescheduled lipid sample collection. Bococizumab/PCSK9 blood samples will be collected from all subjects, but only analyzed, if needed, to help understand the PK, PD, and safety profile of bococizumab in this study population.

Baseline PCSK9 concentration will be defined as the mean of the last two non-missing values prior to and including randomization. If only one non-missing measurement is available, that measurement will serve as the baseline.

Samples for bococizumab and PCSK9, if analyzed, will be analyzed using a validated analytical method in compliance with Pfizer standard operating procedures.

6.3.2. Outcomes Research Endpoints

EuroQol 5-Dimensions (EQ-5D)

The EuroQol 5-Dimension (EQ-5D) is a generic measure of health-related quality of life. The EQ-5D is a subject completed instrument designed to assess impact on quality of life in five domains: mobility, self-care, usual activities, pain/discomfort, and anxiety/depression. Additionally, scores from the five domains may be used to calculate a single index value. The EuroQol EQ-5D Visual Analogue Scale (VAS) is a patient-completed 20 cm scale designed to rate an individual's current health state. The Health State Profile will be administered concurrently with the VAS-HEALTH STATE component of the EuroQol EQ-5D instrument.

The EQ-5D will be administered at Baseline and at Weeks 14, 26, 52, 104, 156, 208 and the subject's last visit (EDC or EOS). If the trial runs longer than 208 weeks, the EQ-5D will be collected every 52 weeks after Week 208.

The baseline values for the EQ-5D health index score and health state score will be the last non-missing value prior to or on the day of randomization.

The health index score will be calculated as per Shaw, Johnson and Coons (2005). Prior to calculating the health index score, the following are calculated.

- I2 = number of item scores equal to 2.
- I3 = number of item scores equal to 3.

The health index score is calculated as follows:

1. The initial health index score is 1.0.
2. If the mobility score:
 - a. is 2, then 0.146016 is subtracted
 - b. is 3, then 0.557685 is subtracted
3. If the self-care score:
 - a. is 2, then 0.1753425 is subtracted
 - b. is 3, then 0.4711896 is subtracted
4. If the usual activities score:
 - a. is 2, then 0.1397295 is subtracted
 - b. is 3, then 0.3742594 is subtracted
5. If the pain/discomfort score:
 - a. is 2, then 0.1728907 is subtracted
 - b. is 3, then 0.5371011 is subtracted
6. If the anxiety/depression score:
 - a. is 2, then 0.156223 is subtracted
 - b. is 3, then 0.4501876 is subtracted
7. If $I2 + I3 > 1$, then $(I2 + I3 - 1)$ times 0.1395949 is added.
8. If $I2 > 1$, then 0.0106868 times the square of $(I2 - 1)$ is subtracted.
9. If $I3 > 1$, then 0.1215579 times $(I3 - 1)$ plus 0.0147963 times the square of $(I3 - 1)$ is added.

Health Care Resource Utilization (HCRU)

HCRU assessments will take place at each visit to collect data on the following:

- *The occurrence, primary and secondary discharge diagnoses, overall length of stay, duration of stay in different medical care units, and discharge disposition for all-cause hospitalizations;*

- *The occurrence, primary and secondary discharge diagnoses, overall length of stay, duration of stay in different medical care units, and discharge disposition for CV hospitalizations;*
- *The occurrence of emergency room visits;*
- *The occurrence of physician office visits;*
- *The occurrence of outpatient rehabilitation visits;*
- *The occurrence of all-cause hospitalizations within 30 days of a previous hospitalization, primary and secondary discharge diagnoses, length of stay, and discharge disposition;*
- *The occurrence of CV hospitalizations within 30 days of a previous hospitalization, primary and secondary discharge diagnoses, length of stay, and discharge disposition.*

The medical care units being assessed for these objectives include:

- *Cardiac Care Unit (CCU);*
- *Medical Intensive Care Unit (MICU);*
- *Neurology Intensive Care Unit (NICU);*
- *Surgical Intensive Care Unit (SICU);*
- *Thoracic Intensive Care Unit (TICU);*
- *Cardiac Step-down Unit;*
- *Pulmonary Step-down Unit;*
- *General ward;*
- *Dialysis Unit;*
- *Chemotherapy Unit;*
- *Infections disease isolation unit;*
- *Other.*

Discharge care disposition entities being evaluated for HCRU include:

- *Home self-care;*
- *Home health care;*
- *Nursing home care/skilled nursing facility;*

- *Rehabilitation facility;*
- *Hospice care;*
- *Death;*
- *And other potential disposition entities.*

6.4. Covariates

The randomization will be stratified by geographic region and complete statin intolerance. These variables will be included as stratification factors in log rank tests and Cox proportional hazards regression models and as covariates in linear models for efficacy endpoints. If the model fitting for the Cox proportional hazards model fails to converge, complete statin intolerance will be removed as a stratification factor.

Geographic region and complete statin intolerance will be obtained from the IRT system.

Complete statin intolerance is a binary variable. Subjects with complete statin intolerance will form one group; the other group will consist of subjects with partial or no statin intolerance.

The geographic regions (5 levels) are:

- USA/Canada: Canada, Puerto Rico, United States of America.
- Latin America: Argentina, Brazil, Chile, Columbia, Mexico, Peru.
- Eastern Europe/Turkey: Czech Republic, Hungary, Poland, Romania, Russia, Slovakia, Turkey.
- Asia: China, India, Japan, Korea, Taiwan, Thailand.
- Rest of World: Australia, Belgium, Denmark, Finland, France, Germany, Ireland, Israel, Italy, Netherlands, New Zealand, Republic of South Africa, Spain, Sweden, Switzerland, United Kingdom.

If a subject changes investigational sites during the study, geographic region will be assigned according to the site at which the subject was randomized.

For all linear models that involve changes from baseline, the baseline value will also be used as a covariate.

7. HANDLING OF MISSING VALUES

For the clinical endpoints, not all subjects will have adjudicated and confirmed events. Subjects who do not experience any of the components of the primary endpoint will be censored on the date of last contact or 01November2016, whichever comes first. The date of last contact is defined as the date of death, if the date is not missing. Otherwise, the date of

last contact is defined as the study discontinuation date, the date of last visit, the date of last telephone contact, the onset date of the last AE, or the randomization date, whichever occurs last. The same censoring will be done for all other clinical endpoints and for time to discontinuation from study. For analyses in the SAS, the date of first dose will be substituted for the randomization date.

Missing values for the Digit Span Forward, Digit Span Backward, Digit Symbol - Coding, Trail Making A and Trail Making B tests and the HVLT will not be imputed. For the Digit Span Forward and the Digit Span Backward, if the maximum number of digits is not reached and the last result is not a zero, the value will be missing.

Missing values for the PHQ-2 and PHQ-9 will not be imputed. If at least one item is missing, the total scores will be missing.

For all other efficacy and safety endpoints, missing values will not be imputed; missing values will remain missing.

For longitudinal analyses of circulating biomarker endpoints, a mixed model repeated measures (MMRM) model will be used for the analyses. As a likelihood method, MMRM models are valid when the data are missing at random (MAR). All subjects with a non-missing baseline value and at least one non-missing post-baseline value will be included in these analyses. Subjects with a missing baseline value will not contribute to the analyses. Consistent with MMRM model fitting, no explicit imputation of missing assessments will be performed.

Percent changes from baseline to last post-baseline value in LDL-C will be analyzed by analysis of covariance (ANCOVA). As a likelihood method, ANCOVA is valid when the data are MAR. Subjects with a non-missing baseline value and at least one non-missing post-baseline value will be included in the analyses. Subjects with a missing baseline value or without a non-missing post-baseline value will not contribute to the analyses.

When forming subgroups, subjects with a missing value on the classifying variable will not be included in a subgroup.

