#### **3.3.4. Active Treatment Period**

At the randomization visit, the subject will be assigned to either active treatment or placebo IP in a blinded fashion. IP will be administered SC by self-injection, or by a trained caregiver, Q2wks during the course of the study, unless there has been an IP dose modification to a frequency of Q4wks ([Section 5.4.1.1](#)). Subsequent visits for assessments of

efficacy, safety, and tolerability will be scheduled according to the [Schedule of Activities](#), unless there has been an IP dose modification to Q4wks, in which case subjects will be seen every 8 weeks, approximately, until the completion of the study.

Subjects may return to the study site for unscheduled visits, or to replenish IP supplies, if necessary. Subjects who discontinue IP will be followed until the completion of the study. Randomized subjects who withdraw from the study will have consented, at the onset of the study, to provide vital status information to the study site at the completion of the study.

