### **6.5.2. Lost to Follow-Up**

Lost to follow-up is defined by the inability to reach the subject by the end of the study only. No subject should be considered lost to follow-up, until the study has been completed. If a subject does not return for a scheduled visit, every effort should be made to contact the subject. Attempts to reschedule the visit should be completed by phone, e-mail, text message, and if necessary, by letter and/or certified mail, in instances where the subject is not responsive to contact attempts. This includes follow-up with persons authorized by the subject as noted above. The study retention team must be contacted, through the retention hotline or delegate, to discuss strategies available for assistance with locating subjects who are potentially lost to follow-up. All efforts to retain a subject, should continue throughout the course of the study and should be documented in the subject's medical source records. Every effort should be made to have the subject complete an EDC or EOS visit and to document subject's vital status, if possible.

If it is determined that the subject has died, the site will use permissible local methods to obtain the date and cause of death. If investigator's use of third-party representative to assist in the follow-up portion of the study has been included in the subject's informed consent, then the investigator may use a Sponsor retained third-party representative to assist site staff with obtaining subject's contact information or other public vital status data necessary to complete the follow-up portion of the study. The site staff and representative will consult publicly available sources, such as public health registries and databases, in order to obtain updated contact information. If after all attempts, the subject remains lost to follow-up, then

the last known alive date as determined by the investigator should be reported and documented in the subject's medical records.

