## **7. ASSESSMENTS**

Every effort should be made to ensure that the protocol required tests and procedures are completed as described. However it is anticipated that from time to time there may be circumstances, outside of the control of the investigator, which may make it unfeasible to perform the test. In these cases the investigator will take all steps necessary to ensure the safety and well-being of the subject. When a protocol required test cannot be performed, the investigator will document the reason for this and any corrective and preventive actions which he/she has taken to ensure that normal processes are adhered to as soon as possible. The study team will be informed of these incidents in a timely fashion.

In order to completely and accurately assess the primary and secondary clinical efficacy endpoints and the safety profile of the treatment groups, the vital status of each randomized subject must be obtained at the completion of the study. The occurrence of potential clinical outcome events as defined in [Section 2.2](#) will trigger the compilation of a dossier that includes anonymized supporting medical record information that will be sent to the clinical Adjudication Committee.

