In addition, the sample size in certain subgroups, including diabetic subjects with no prior CVD event, may be modified or the trial duration may be extended to improve the likelihood that the estimated hazard ratios in the subgroups are less than one. Prior to the end of enrollment, the sponsor will perform a blinded assessment of the probabilities, assuming a hazard ratio of 0.75. If one or more of the probabilities are too small, the number of subjects in the corresponding subgroups may be modified, possibly increasing the total enrollment to do so. Prior to the end of the study, the sponsor will include a second blinded assessment of the probabilities. If one or more of these probabilities are too small, the duration of the trial may be extended. If the latter modification is made, the criterion for stopping the trial will include accruing 35 primary endpoint events in the corresponding subgroups. These decisions will be documented in the Trial Master File.

The study may be terminated early following an interim analysis (IA) for clinical benefit. This IA will be performed by a group external to the sponsor and reviewed by the DMC when both an adjudicated and confirmed primary endpoint event has occurred in 75% of the

required number of subjects, and an adjudicated and confirmed composite key secondary endpoint of cardiovascular death, non-fatal MI, or non-fatal stroke has occurred in 75% of the expected number of subjects (288). This IA may occur before 12 months after the last randomization. The non-binding decision rule is to stop the trial if the two-sided p-values for the primary endpoint and the above composite key secondary endpoint are at most 0.001. The decision to stop or continue the trial will be made by the DMC without any input from the Sponsor; the Sponsor will remain blinded and will not be exposed to any of these analyses. The Heybittle-Peto method with $\alpha=0.001$ will be used to control the experimentwise Type 1 error rate, resulting in an adjustment to the final alpha of 0.00002.

Randomized subjects who withdraw from the study will have consented, at the onset of the study, to provide vital status information to the study site at the completion of the study.

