8.2.1. Analysis of Primary Endpoint

The primary objective is to demonstrate superiority of bococizumab over placebo with respect to the primary endpoint, the time from randomization to the first adjudicated and confirmed occurrence of a major cardiovascular event, a composite endpoint which includes CV death, non-fatal MI, non-fatal stroke, and hospitalization for unstable angina needing urgent revascularization (as defined in [Appendix 1.2](#)). Subjects who discontinue randomized study medication prematurely and have not withdrawn consent will continue to be followed in the study to assess the occurrence of endpoints. Subjects who do not experience any of the components of the primary endpoint will be censored on the date of last contact or

01 November 2016, whichever comes first. The date of last contact is defined as the date of death, if the date is not missing. Otherwise, the date of last contact is defined as the study discontinuation date, the date of last visit, the date of last telephone contact, the onset date of the last AE, or the randomization date, whichever occurs last.

Primary analysis

The primary endpoint will be analyzed in the FAS using a log rank test stratified by geographic region and complete statin intolerance. The overall alpha level for this trial is 0.05. The two-sided alpha level for this log rank test will be adjusted for DMC reviews of all-cause death (see [Section 3](#)) and the interim analysis for clinical benefit (see [Section 3](#)) so that a two-sided alpha of 0.04898 will be used.

Analyses supportive of the primary analysis

A Cox proportional hazards model will be fit with the treatment group as a covariate and geographic region and complete statin intolerance as stratification factors. If the model fitting fails to converge, complete statin intolerance will be removed as a stratification factor. The hazard ratio will be presented along with a 95% confidence interval. The goodness of fit of the Cox proportional hazards regression model will be assessed by visual inspection of Arjas plots. Kaplan-Meier estimates of time to first major cardiovascular event will be plotted.

Sensitivity analyses

It is assumed that there will be a premature study discontinuation rate of 1% per year.

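### For all-cause death, a death found after a subject leaves is counted at its date, but a subject found alive other than by visit or telephone stays censored at departure

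*SAP*

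**What the plan says.** **The censoring rule.** SAP section 7 censors subjects without an event at the earlier of last contact and 01November2016. It defines last contact in two steps, and SAP section 8.2.1 repeats the definition for the primary endpoint:

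- For a subject known to be dead: "The date of last contact is defined as the date of death, if the date is not missing".
- For everyone else, the latest of several dates is used: "the date of last contact is defined as the study discontinuation date, the date of last visit, the date of last telephone contact". Last adverse event onset and randomization complete that list.

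Section 8.2.1 goes no further than the primary endpoint. The extension to other endpoints is in section 7: "The same censoring will be done for all other clinical endpoints and for time to discontinuation from study". All-cause death is one of these (SAP sections 6.1.3 and 8.2.2).

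**Vital status.**

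- Protocol section 7 says that "the vital status of each randomized subject must be obtained at the completion of the study".
- SAP section 2.1 says: "Randomized subjects who withdraw from the study will have consented, at the onset of the study, to provide vital status information". Protocol section 3.3.4 says the same.
- Protocol section 6.5.2 tells sites what to do once a death is established: "If it is determined that the subject has died, the site will use permissible local methods to obtain the date and cause of death". For subjects who stay lost after every attempt, "the last known alive date as determined by the investigator should be reported and documented". The same section allows public registries and a third-party representative to be used.

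No vital-status date or last-known-alive date appears in the definition of last contact.

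**The concern.** Two subjects who leave the study on the same day can receive different follow-up purely because of what happened to them later. If the end-of-study search finds that one has died, the death counts on its date. If the search finds the other alive through a source that is neither a visit nor a telephone contact, that subject's time at risk ends at departure. Departed subjects can then add deaths without the matching survival time.

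SAP section 8.1.1.1 says that the log rank test, the Cox model and the Kaplan-Meier estimate all rest on censoring being unrelated to the risk of the event. Here the amount of follow-up can be set by the event itself. The only check for informative censoring, the multiple imputation in section 8.2.1, is confined to the primary endpoint.

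What is at stake is mainly the absolute mortality rate. The SAP reports all-cause death per 100 subject-years, tabulates causes of death with event rates, and plots Kaplan-Meier curves. The between-arm comparison would be touched only if one arm lost more subjects than the other.

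**Working it through.** The documents give no figure for all-cause death or for the effect of this rule, so there is none to reproduce. The 508-event target concerns the primary endpoint and is not affected.

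**Inputs**

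- 11,000 subjects, 5,500 per arm; recruitment over 2.5 years with half in the last six months (Protocol section 9.1). Uniform entry within each half is assumed.
- Loss or withdrawal rate *w*: 1% per year is the planned premature discontinuation rate (Protocol section 9.1, SAP section 8.2.1); 0.5% per year is an assumed lower value.
- First entry to 01November2016: not stated. Assumed 3.0 years, with 3.18 years as a limit (original protocol date, 26 August 2013, to 01November2016).
- Death rate: not stated. Assumed 0.8 to 1.6% per year.
- *p_d*, the share of post-departure deaths that are found, and *p_s*, the share of survivors credited after departure: neither is stated. The upper bound takes *p_d* = 1 and *p_s* = 0.

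**Step 1: follow-up available.** Let *u* be the time from entry to the cut. With a 3.0-year cut, *u* is uniform on 1.0 to 3.0 for half the subjects and on 0.5 to 1.0 for the other half.

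- E(*u*) = 0.5 × (3.0 − 1.0) + 0.5 × (3.0 − 2.25) = 1.375 years.
- E(*u*²) = 0.5 × (27 − 1)/6 + 0.5 × (1 − 0.125)/1.5 = 0.5 × 4.333 + 0.5 × 0.583 = 2.458.

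**Step 2: share of person-time after departure.** To first order, *f* = *w* × [E(*u*²)/2] / E(*u*) = *w* × 1.229/1.375 = 0.894*w*. That is 0.45% at 0.5% per year and 0.89% at 1% per year.

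Integration with exponential death and loss gives nearly the same:

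- Death 0.8%, loss 1% per year: 15,017 person-years in full, 14,885 used. Difference 132; ratio 15,017/14,885 = 1.0089.
- Death 1.6%, loss 0.5% per year: 14,911 in full, 14,846 used. Difference 65; ratio 14,911/14,846 = 1.0044.

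Across these assumptions 74 to 149 subjects leave early. They account for 0.5 to 2.1 later deaths, out of totals of 0.008 × 15,017 = 120 to 0.016 × 14,911 = 239.

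**Step 3: overstatement of the death rate.** To first order the relative bias is *f* × (*p_d* − *p_s*).

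| Later deaths found | Survivors credited | Loss 0.5%/yr | Loss 1%/yr |
|---|---|---|---|
| all | none | 0.44% | 0.88 to 0.89% |
| half | none | 0.22% | 0.44% |
| all | 80% | 0.2 × 0.44 = 0.09% | 0.2 × 0.88 = 0.18% |
| equal shares | equal shares | 0 | 0 |

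With the 3.18-year cut, mean follow-up is 1.555 years and the first row becomes 0.47 to 0.95%. Had the trial run its planned 3.9 years (mean follow-up 0.5 × 2.9 + 0.5 × 1.65 = 2.275 years), it would be about 1.25% at 1% per year. The 01November2016 cap rules out that horizon.

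**Step 4: hazard ratio for all-cause death.** With equal loss the inflation cancels and a true ratio of 1 stays at 1.000. With an assumed 1.0% against 0.5% per year it becomes 1.0088/1.0044 = 1.004, against the arm with more loss. Reversed, it is 0.996.

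**The case against.** The strongest reply is that the gap is narrow. Deaths found by the vital-status check do count. A survivor reached by visit or telephone is credited, because the latest date is used, and SAP version 2.0 added last visit and last telephone contact to the definition (SAP section 1.1). Subjects who stop drug but remain in the study keep contact by visit or telephone (Protocol section 6.4.6). What is left is subjects who leave before 01November2016 and are found alive only by another route. The calculation also credits no survivors, which makes it a worst case. All of this stands, and it is why the size is given as an upper bound.

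Three stronger readings are tempting, and the documents do not support them.

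- A reader might infer that the analysis disregards vital status. It does not: found deaths and survivors contacted directly both enter.
- A reader might infer that data held by the trial are thrown away. That is not shown. The vital-status requirement names no date, the last-known-alive date is asked for only in subjects who stay lost, and it goes in the medical records. No case report form field is named.
- Protocol section 6.5.2 allows lost status only at study completion. A reader might infer that lost subjects are therefore carried event-free to the cut. That depends on which discontinuation date sites record for them, which the documents do not say. If it were so, lost subjects would fall outside the mechanism described here and the bound would shrink to withdrawals.

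It can also be said that the fix is partial, since composites keep the asymmetry through their death component. That is true, including for the two key secondary composites that contain all-cause death. The effect is diluted there. For the primary composite, if 10 to 30% of events are assumed to be cardiovascular deaths, the rate is overstated by 0.09 to 0.26% at 1% loss per year, and a hazard ratio of 0.750 is unchanged. Extending composite follow-up to a vital-status date would be worse, because non-fatal events were not ascertained to that date.

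**Conclusion.** The point holds and is minor. The rule in SAP section 7 can make mortality follow-up depend on outcome, and no planned sensitivity analysis looks at this for all-cause death. As an upper bound, the all-cause death rate is overstated by about 0.4 to 0.9% relative. This rests on an assumed loss of 0.5 to 1% per year, about 3 years from first entry to the cut, every later death found and no survivor credited. The bias shrinks in proportion as survivors are credited, and it vanishes if deaths and survivors are found equally often.

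A reader might go further and infer a biased mortality comparison. The documents give no imbalance in loss between arms, and even an assumed twofold imbalance moves a null hazard ratio only to 1.004 or 0.996. All-cause death by itself is also outside the fixed testing sequence, so no confirmatory decision turns on this.

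**What to change.** In SAP section 7, for all-cause death only, censor at the later of the current date of last contact and any recorded vital-status or last-known-alive date, capped at 01November2016. Keep the current rule for every endpoint with a non-fatal component. Report by arm the number of deaths dated after the last visit or telephone contact, so that the reader can see whether the asymmetry had any effect.

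The cost is one sentence and one derivation before unblinding, in a definition that version 2.0 had already revised. Reported death rates may fall by less than 1% relative. The remedy is limited by the data: a known-alive date may be missing for some subjects. After a subject also withdraws consent for disclosure, Protocol section 6.5.1 stops further data collection, so vital status could come only from public sources where local law allows.
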